12.1.2. Primary Endpoint for CRT-D Treated Subjects

The primary endpoint for CRT-D treated subjects is:

- Composite rate of first appropriately treated ventricular arrhythmia (by anti-tachycardia pacing [ATP] or shock) or life-threatening symptoms associated to ventricular arrhythmia (defined as hemodynamic instability which requires treatment), whichever comes first under MADIT Arm B or C programming conditions in a study population with a majority of Japanese subjects

Based on the MADIT RIT study⁴, we estimate that 3% of the CRT-D treated subjects will present a first appropriately treated ventricular arrhythmia associated symptom (by ATP or shock) within one year.

12.1.2.1. Hypotheses

The null and alternative hypotheses are as follows:

H_0 : The ventricular arrhythmia associated symptoms free-rate from 0-12 months $\leq 87.0\%$

H_A : The ventricular arrhythmia associated symptoms free-rate from 0-12 months $> 87.0\%$

The null hypothesis (H_0) will be rejected if the lower one-sided 97.5% confidence bound for the ventricular arrhythmia associated symptoms free-rate is greater than the performance goal of 87.0%.

12.1.2.2. Statistical Methods

When the final study subject reaches the final CIP required follow-up visit, the primary analysis will be performed based on the Kaplan-Meier method for the estimation of the 12-month ventricular arrhythmia associated symptoms free-rate, including the lower 97.5% confidence bound (computed based on log-log methodology). This Kaplan-Meier analysis will begin at the time of implant. Subjects that withdraw consent or are lost-to-follow-up prior to the 12-month endpoint evaluation will be censored at their date of last contact. All subjects actively enrolled will be included in the endpoint analysis.

The null hypothesis will be rejected and the endpoint considered met if the lower 97.5% confidence bound for the ventricular arrhythmia associated symptoms free-rate at 12-months is greater than 87.0%.

Additionally, a Kaplan-Meier survival time-to-event curve along follow-up will be provided.

The primary analysis above will be performed for CRT-D and ICD cohorts combined as well as for CRT-D treated subjects separately.

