Statistical Test Method	
Sample Size Methodology:
 
 Sample size for each primary endpoint was calculated using exact binomial methods for comparison of a single proportion to a performance goal. 
Analysis Methods:
 
 For ICD treated subjects, the ventricular arrhythmia associated symptoms free-rate from implant will be calculated as the proportion of actively enrolled subjects without an appropriately treated ventricular arrhythmia associated symptom through 12 months after implant. The null hypothesis will be rejected and the endpoint considered met if the lower one-sided 97.5% confidence bound for the proportion of subjects with no appropriately treated ventricular arrhythmia associated symptoms is greater than 85.0%. For CRT-D treated subjects, the ventricular arrhythmia associated symptoms free-rate from implant will be calculated as the proportion of actively enrolled subjects without an appropriately treated ventricular arrhythmia associated symptom through 12 months after implant. The null hypothesis will be rejected and the endpoint considered met if the lower one-sided 97.5% confidence bound for the proportion of subjects with no appropriately treated ventricular arrhythmia associated symptoms is greater than 87.0%.

Heart Failure Indication and Sudden Cardiac Death Prevention Trial Japan
HINODE

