Statistical Test Method (continued)	
 • The primary endpoints above will be performed for ICD and CRT-D cohorts combined (primary analysis) as well as for ICD and CRT-D treated subjects separately (for descriptive purpose). • For PM/CRT-P treated subjects, the all-cause mortality free-rate (survival rate) from implant will be calculated as the proportion of actively enrolled subjects who are alive 12 months after implant. The null hypothesis will be rejected and the endpoint considered met if the lower one-sided 97.5% confidence bound for the proportion of subjects with no death is greater than 80.0%. • For Non-device subjects (ESC Guideline 2016 Indicated but not implanted), the all-cause mortality free-rate (survival rate) from enrolment will be calculated as the proportion of actively enrolled subjects who are alive 12 months after enrolment. The null hypothesis will be rejected and the endpoint considered met if the lower one-sided 97.5% confidence bound for the proportion of subjects with no death is greater than 80.0%. • Exploratory analyses for ICD and CRT-D Cohorts combined versus Non-Device Cohort (ESC Guideline 2016 Indicated but not implanted): propensity score matching comparison of all-cause mortality rate and composite rate of HF events between pooled cohorts with device (ICD and CRT-D) versus the Non-Device Cohort regarding 7 risk factors at baseline (NYHA Class III or IV, renal dysfunction [chronically BUN >26 mg/dL / ≥ 9.28 mmol/L], diabetes type I and II, chronic atrial fibrillation [permanent or persisting according to ESC Guideline 2016], prior MI, age >70 years, smoking today or during last 5 years). 
Further details on analytical methods can be found in Section 12 of the CIP

Sample Size Parameters	
ICD Treated Subjects:
 
The minimum required sample size to statistically power the ventricular arrhythmia associated symptoms free-rate through 12 months post implant is 117 subjects. Sample size was calculated assuming a 95.0% ventricular arrhythmia associated symptoms free-rate, a performance goal of 85.0%, one-sided alpha level of 0.025, 90% power, and 20% attrition.

Heart Failure Indication and Sudden Cardiac Death Prevention Trial Japan
Hinode

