7.1. Primary Endpoints

Defibrillator Cohort (including ICD and CRT-D Cohorts):

- Composite rate of first appropriately treated ventricular arrhythmia (by ATP or shock) or life-threatening symptoms associated to ventricular arrhythmia (defined as hemodynamic instability which requires treatment), whichever comes first under MADIT Arm B or C programming conditions in a study population with a majority of Japanese subjects

PM/CRT-P Cohort:

- All-cause mortality in subjects with a maximum of 3 risk factors (analyzed for MADIT II data⁷)

Non-device Cohort (ESC Guideline 2016 Indicated but not implanted subjects):

- All-cause mortality in the subject cohort with 2 to 5 predefined SCD driving risk factors

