12.1.1.2. Statistical Methods

When the final study subject reaches the final CIP required follow-up visit, the primary analysis will be performed based on the Kaplan-Meier method for the estimation of the 12-month ventricular arrhythmia associated symptoms free-rate, including the lower 97.5% confidence bound (computed based on log-log methodology). This Kaplan-Meier analysis will begin at the time of implant. Subjects that withdraw consent or are lost-to-follow-up prior to the 12-month endpoint evaluation will be censored at their date of last contact. All subjects actively enrolled will be included in the endpoint analysis.

The null hypothesis will be rejected and the endpoint considered met if the lower 97.5% confidence bound for the ventricular arrhythmia associated symptoms free-rate at 12 months is greater than 85.0%.

Additionally, a Kaplan-Meier survival time-to-event curve along follow-up will be provided.

The primary analysis above will be performed for CRT-D and ICD cohorts combined as well as for ICD treated subjects separately.

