12.1.6. Sample Size

The pre-specified primary endpoints sample sizes are outlined in **Error! Reference source not found.** The minimum required sample sizes to sufficiently power each primary endpoint at 90% and account for up to 20% attrition are lower than the final sample sizes.

The final sample sizes for the device cohorts (ICD: 117 to 270 subjects; CRT-D: 95 to 250 subjects; PM/CRT-P: 172 to 200 subjects) will ensure that there will be a sufficient number

of subjects to evaluate each primary endpoint, as well as provide ample data to characterize the safety, performance and efficacy profiles based on secondary and additional endpoints.

The final sample size for the non-device cohort (Non-device [ESC Guideline 2016 Indicated but not implanted]: 172 to 300 subjects) will ensure that there will be a sufficient number of subjects to compare the rate of sudden cardiac death in the non-device cohort with the rate of appropriately treated ventricular arrhythmias or sudden cardiac death in the defibrillator cohort (ICD, CRT-D).

In case of low enrollment rates, enrollment may be closed after the statistically required calculated minimum sample size was completed.

Table 12.1-1: Endpoint Sample Size Estimates

Endpoint	Measurement	Performance Goal Hypotheses ¹	Expected Performance ²	Power	Number of Subjects	
					Needed for Analysis	Required Minimum Sample size Enrolled for ≤20% Attrition
Primary Endpoint for ICD Treated Subjects	Ventricular arrhythmia ³ associated symptoms free-rate from 0 to 12 months	H_0 : Rate ≤ 85.0% H_A : Rate > 85.0%	95.0%	90%	93	117
Primary Endpoint for CRT-D Treated Subjects	Ventricular arrhythmia ³ associated symptoms free-rate from 0 to 12 months	H_0 : Rate ≤ 87.0% H_A : Rate > 87.0%	97.0%	90%	76	95
Primary Endpoint for PM/CRT-P Treated Subjects	All-cause mortality free-rate (survival rate) from 0 to 12 months	H_0 : Rate ≤ 80.0% H_A : Rate > 80.0%	90.0%	90%	137	172
Primary Endpoint for Non-device Subjects (ESC Guideline 2016 Indicated but not implanted)	All-cause mortality free-rate (survival rate) from 0 to 12 months	H_0 : Rate ≤ 80.0% H_A : Rate > 80.0%	90.0%	90%	137	172

¹ Hypothesis test based on a one-sided alpha level of 0.025; clinically accepted delta of 10%, subtracted from expected performance

² Determined from prior comparable studies

³ Appropriately treated

CRT-D = cardiac resynchronization therapy-defibrillator; ICD = implantable cardioverter-defibrillator;

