PM = pacemaker; CRT-P = cardiac resynchronization therapy-pacemaker.

Sample sizes for primary endpoints were calculated employing exact binomial methods in nQuery + nTerim 3.0.

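### The protocol contradicts itself on which defibrillator test is confirmatory, and the combined ICD plus CRT-D test has no single performance goal (85% in Section 12.1.1.2, 87% in Section 12.1.2.2)

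*Combined protocol and SAP*

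**What the plan says.** **Role of each test.** Section 7.1 defines the arrhythmia endpoint for one group, the "Defibrillator Cohort (including ICD and CRT-D Cohorts"). The synopsis, under Statistical Test Method, says the analysis is "performed for ICD and CRT-D cohorts combined (primary analysis) as well as for ICD and CRT-D treated subjects separately (for descriptive purpose"). The same synopsis states hypotheses, goals and success rules only for ICD (85%) and CRT-D (87%) separately, and sets the minimum of 556 subjects so that each cohort's primary endpoint is powered.

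**Section 12.** Sections 12.1.1.1 and 12.1.2.1 give ICD and CRT-D their own null hypotheses. Table 12.1-1 gives each 90% power, and Section 12.2.3 reserves hypothesis testing for the primary endpoints. None of these calls the separate tests descriptive. The ICD section, whose goal is 85%, ends: "The primary analysis above will be performed for CRT-D and ICD cohorts combined as well as for ICD treated subjects separately". The CRT-D section, whose goal is 87%, ends: "The primary analysis above will be performed for CRT-D and ICD cohorts combined as well as for CRT-D treated subjects separately". No hypothesis, goal or sample size for the combined cohort appears anywhere.

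**Bound and sizing.** Sections 12.1.1.2, 12.1.2.2, 12.1.3.2 and 12.1.4.2 all use a 12-month Kaplan-Meier estimate, "including the lower 97.5% confidence bound (computed based on log-log methodology"), with withdrawn and lost subjects censored at last contact. Sizing used a different method: "Sample sizes for primary endpoints were calculated employing exact binomial methods in nQuery + nTerim 3.0". The synopsis describes the estimate as a simple proportion of the actively enrolled.

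**The concern.** A performance-goal study turns on one number fixed in advance. Here the analysis labelled primary inherits two numbers, one from each section that mentions it, and the analyses labelled descriptive are the only ones with complete decision rules. If the synopsis governs, the confirmatory test has no goal. If Section 12 governs, the descriptive label in the synopsis is wrong. The same combined data could be reported as meeting or missing the endpoint according to which section is cited.

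A second, smaller gap sits in the rule itself. With no events the Kaplan-Meier estimate is 1 and Greenwood's variance is 0, so log(−log S) does not exist and there is no bound to compare with the goal. No passage says how that result is scored. The protocol defers only secondary, additional and propensity-score methods to a separate SAP (Sections 12.1.5, 12.3 and 12.3.1), not this rule.

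**Working it through.** **1. The plan's own sizes reproduce.** Inputs from Table 12.1-1: one-sided alpha 0.025, 90% power, 20% attrition. Smallest n at which the exact binomial test has at least 90% power:

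- CRT-D, 97% against 87%: n = 76, success at 72 or more event-free, alpha 0.0241, power 92.2%; 76/0.8 = 95 enrolled.
- ICD, 95% against 85%: n = 93, success at 86 or more, alpha 0.0235, power 90.6%; 93/0.8 = 116.25, rounded up to 117.
- PM/CRT-P and non-device, 90% against 80%: n = 137, alpha 0.0245, power 91.0%; 137/0.8 = 171.25, rounded up to 172.

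All match the table.

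**2. The two goals on the same combined data.** With complete follow-up, n subjects and d events, S = 1 − d/n and the standard error of log S is se = √[d/(n(n − d))]. The log-log lower bound is L = S^exp(1.96·se/|ln S|).

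At the combined minimum, n = 117 + 95 = 212. For d = 17, S = 0.9198, se = 0.0203 and L = 0.874.

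| Events of 212 | Lower bound | Goal 85% | Goal 87% |
|---|---|---|---|
| 17 | 0.874 | met | met |
| 18 | 0.869 | met | not met |
| 21 | 0.852 | met | not met |
| 22 | 0.847 | not met | not met |

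At the maximum, n = 270 + 250 = 520, the limits are 61 events (85%) and 52 (87%). The exact binomial bound gives the same four limits. A size-weighted goal, (117 × 85 + 95 × 87)/212 = 85.9%, would allow 19 of 212, so a third reading gives a third answer.

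**3. How often the goals disagree at 212.** This is P(18 ≤ d ≤ 21). At the planned rates the combined event-free rate is (117 × 0.95 + 95 × 0.97)/212 = 95.9%, and the probability is 0.003. The protocol gives no other rate, so the following true rates are assumptions:

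| True combined event-free rate | P(18 to 21 events) |
|---|---|
| 89% | 0.26 |
| 90% | 0.34 |
| 91% | 0.36 |
| 92% | 0.30 |

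**4. Zero events.** Full follow-up: 0.97^95 = 5.5% for CRT-D at 95 enrolled. For 20% attrition, assume a constant dropout hazard μ = −ln 0.8 and event hazard λ = −ln 0.97. A subject shows no event with probability 1 − [λ/(λ + μ)]·(1 − e^−(λ+μ)) = 0.9731, and 0.9731^95 = 7.5%. Elsewhere the chance is far smaller:

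- CRT-D at 250 enrolled: 0.97^250 = 0.05%.
- Combined 212: 0.97^95 × 0.95^117 = 0.014%.

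Simulated Kaplan-Meier log-log power for CRT-D at 95 enrolled is 93% with full follow-up and 89% at 20% attrition if zero events counts as met. If it does not, power is 88% and 82%.

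**5. A bound that exists at zero events.** With Y subjects still at risk at 12 months, the exact lower bound is 0.025^(1/Y). It is 0.872 at Y = 27, 0.852 at Y = 23 and 0.805 at Y = 17, the smallest Y that clear 87%, 85% and 80%. At Y = 95 it is 0.962.

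**The case against.** The strongest reply is that the synopsis does settle the matter, because it names the combined analysis as primary. That is right as far as it goes, so the defect is a contradiction and not silence. But naming the test does not supply its goal, and Section 12, to which the synopsis refers for analytical detail, gives two.

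It is also fair that the two goals rarely disagree at the planned rates (0.3%), and that the 26% to 36% rests on true rates the protocol does not propose. Both stand. A threshold is fixed in advance for the case where the planning rates are wrong.

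Four stronger readings are tempting and the documents do not support them.

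- **That exact sizing with log-log analysis leaves the cohorts undersized.** With complete data the two rules allow the same number of events at 95, 117 and 172 enrolled (5, 9 and 23). The sizes labelled as needed for analysis are not the analysed sample, since all actively enrolled subjects contribute follow-up until censored.
- **That the zero-event gap is the main threat.** Under the synopsis it falls on a descriptive analysis. No passage scores zero events as failure, and the exact bound at 0 of 95 is 96.2%.
- **That the synopsis proportion would make the mortality cohorts fail through attrition alone.** This needs lost subjects to count as not alive. Sections 12.1.3.2 and 12.1.4.2 censor them instead.
- **That the choice can be made only after the data are seen.** Section 12.3.7 allows an amended SAP before database lock, and no interim analysis is planned. Protection is incomplete, because a sponsor team reviews reported events as they arrive (Section 22.1), which is a reason to amend early.

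**Conclusion.** The point holds. The synopsis and Section 12 conflict on which defibrillator test is confirmatory, and the combined test has two candidate goals. The consequence is a band of 18 to 21 events in 212, or 53 to 61 in 520, in which the verdict depends on the section cited. These limits assume complete follow-up.

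The zero-event gap is real but secondary. It is material only if the separate CRT-D test is confirmatory and enrolment stays near 95, and its upper figure also assumes 20% attrition spread over the year. In that case, with zero events counted as met, CRT-D power is about 89%, roughly one point below the stated 90%. The stated sample sizes are not in error. The synopsis estimator is loose wording to align, with no demonstrated effect on results.

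**What to change.** 1. In the synopsis (Statistical Test Method), Sections 12.1.1.2 and 12.1.2.2 and Table 12.1-1, state which defibrillator test is confirmatory. If it is the combined one, pre-specify its single goal and label the ICD and CRT-D tests descriptive throughout, including Sections 12.1.1.1 and 12.1.2.1. If it is the separate ones, remove the primary and descriptive labels from the synopsis sentence.
2. Add one line to the log-log rule in all four methods sections: if no event occurs by 12 months, use the exact bound 0.025^(1/Y), Y being the subjects still at risk at 12 months; the endpoint is met if this exceeds the goal. If the separate CRT-D test is confirmatory, restate its power as about 89% at 95 enrolled with 20% attrition.
3. Replace the synopsis proportion of actively enrolled subjects with the Section 12 Kaplan-Meier 12-month estimate.

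The cost is a wording amendment and one analysis convention, with no enrolment beyond the stated minima. It should be made well before database lock.

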12.1.3. Primary Endpoint for PM/CRT-P Treated Subjects

The primary endpoint for PM/CRT-P treated subjects is:

- All-cause mortality in subjects with a maximum of 3 risk factors (analyzed for MADIT II data⁷)

Based on previous CARE-HF study⁸, we estimate that 10% of the PM/CRT-P treated subjects will present an all-cause mortality within one year.

12.1.3.1. Hypotheses

The null and alternative hypotheses are as follows:

H_0 : The all-cause mortality free-rate (survival rate) from 0-12 months $\leq 80.0\%$

H_A : The all-cause mortality free-rate (survival rate) from 0-12 months $> 80.0\%$

The null hypothesis (H_0) will be rejected if the lower one-sided 97.5% confidence bound for the all-cause mortality free-rate is greater than the performance goal of 80.0%.

12.1.3.2. Statistical Methods

When the final study subject reaches the final CIP required follow-up visit, the primary analysis will be performed based on the Kaplan-Meier method for the estimation of the 12-month all-cause mortality free-rate (survival rate) including the lower 97.5% confidence bound (computed based on log-log methodology). This Kaplan-Meier analysis will begin at the time of implant. Subjects that withdraw consent or are lost-to-follow-up prior to the 12-month endpoint evaluation will be censored at their date of last contact. All subjects actively enrolled will be included in the endpoint analysis.

The null hypothesis will be rejected and the endpoint considered met if the lower 97.5% confidence bound for the all-cause mortality free-rate (survival rate) at 12 months is greater than 80.0%.

Additionally, a Kaplan-Meier survival time-to-event curve along follow-up will be provided.

12.1.4. **Primary Endpoint for Non-device Subjects (ESC Guideline 2016 Indicated but not implanted)**

The primary endpoint for Non-device subjects (ESC Guideline 2016 Indicated but not implanted) is:

- All-cause mortality in the subject cohort with 2 to 5 predefined SCD driving risk factors.

Based on the MADIT II study², we estimate that 10% of the Non-device subjects (ESC Guideline 2016 Indicated but not implanted) will present an all-cause mortality within one year.

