Key Exclusion Criteria (continued)	
Additional Exclusion Criteria for the ICD and CRT-D Cohorts:
 
 1. CRT implanted in subjects with a QRS duration <130 ms 2. Subjects who have recovered from a ventricular arrhythmia causing hemodynamic instability. 3. NYHA Class IV (for ICD subjects only) 4. Existing or previously implanted ICD, CRT-P, CRT-D, or pacemaker device system. 
Additional Exclusion Criteria for the PM/CRT-P Cohort:
 
No additional Exclusion Criteria for the PM/CRT-P Cohort.
 
Additional Exclusion Criteria for the Non-device Cohort (ESC Guideline 2016 Indicated but not implanted):
 
 1. Subjects who have recovered from a ventricular arrhythmia causing hemodynamic instability 2. Any ICD or CRT-D, PM or CRT-P device implanted at any time prior to enrollment.
---	--

Statistical Methods

Primary Statistical Hypothesis	
ICD Treated Subjects:
 
Ventricular arrhythmia associated symptoms free-rate from implant through 12 months post implant is greater than the pre-specified performance goal of 85.0%
 $H_0: \pi \leq 85.0\%$ $H_A: \pi > 85.0\%$ 
CRT-D Treated Subjects:
 
Ventricular arrhythmia associated symptoms free-rate from implant through 12 months post implant is greater than the pre-specified performance goal of 87.0%
 $H_0: \pi \leq 87.0\%$ $H_A: \pi > 87.0\%$
---------------------------------------	---

Heart Failure Indication and Sudden Cardiac Death Prevention Trial Japan
Hinode

Primary Statistical Hypothesis (continued)	
PM/CRT-P Treated Subjects: All-cause mortality free-rate (survival rate) from implant through 12 months post implant is greater than the pre-specified performance goal of 80.0% $H_0: \pi \leq 80.0\%$ $H_A: \pi > 80.0\%$
 
Non-device Subjects (ESC Guideline 2016 Indicated but not implanted) All-cause mortality free-rate (survival rate) from enrolment through 12 months after enrolment is greater than the pre-specified performance goal of 80.0% $H_0: \pi \leq 80.0\%$ $H_A: \pi > 80.0\%$

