If a center wishes to exceed these limits, the center must obtain prior approval from the sponsor or sponsor's delegated representative.

As soon as a minimum of 556 eligible subjects are entered into the study database, the closure of enrolment can begin. All sites will be informed that enrolment has closed. After closure of enrolment has been communicated, sites must obtain approval from the sponsor or the sponsor's delegated representative for all remaining subjects who are consented but who are not yet enrolled into the study database.

A maximum of 950 subjects will be allowed to be followed and entered into the study database.

11. Study Methods

11.1. *Data Collection*

Details for data collection are shown in Table 11.1-1. Data collection will take place at the following time points:

- Enrolment and Consenting Clinic Visit (Day 0, 0 to 45 days post implant procedure, alternative minimum > 3months post MI, PCI, or CABG required). The date of signature on the informed consent form is the time point of enrolment.
- Six-monthly Visit (180 ± 60 days post enrolment and multiplies until Close-out Visit) (required)
- Re-implant or new device implant post enrolment (optional)
- Interim Visit and Event Report (SAE/SADE related clinical care visit) (Following study site specific SOC, optional)
- Close-out Clinic Visit (see table 8.1-1) (required)

All clinic visits that occur outside the specified protocol visit window will be classified as "Unscheduled CIP Visits". Unscheduled visits triggered by a specific event (e.g. adverse event, Latitude alert, patient request etc.) and not by standard routine control (e.g. device check-up standard by the institution, wound check, standard echo or ECG, blood analysis etc.) must be documented.

CIP defined visits that occur outside the specified visit window will be documented as a CIP deviation.

All data collected according to the Data Collection Requirements (Table 11.1-1) and specified in Sections 11.2 to 11.9 are to be appropriately noted in the eCRF.

Table 11.1-1: Data Collection Requirements

Procedure/Assessment	Enrolment and Consenting Clinic Visit	Follow-Up Visits			

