11.3. Informed Consent

During the Enrolment and Consenting Visit (Section 11.4), a qualified center representative will review the consent with a potential subject. The subject will be encouraged to ask any questions about the study. All questions from the subject should be addressed prior to the subject signing the informed consent. If the subject signs the informed consent, a signed copy should be provided to the subject and the original should be filed in the electronic or paper medical records. Documentation of the consent process by the person obtaining consent should be filed in the subject study file. No study-specific data collection of any procedure should be conducted prior to consent.

11.4. Enrolment and Consenting Visit (Day 0, 0 to 45 days post implant procedure, alternative >90 days post MI)

Prior to initiating any study procedures, the investigator must ensure that appropriate informed consent has been signed and dated (Section 21). Subjects will sign and date the ICF post successful implant or minimum 3 months post MI, PCI, or CABG.

Subjects who meet all of the entry criteria and consent to the evaluation are eligible. The enrolment for this registry will occur up to 45 calendar days after the device system implantation.

Subjects are considered enrolled after they have met all inclusion criteria, none of the exclusion criteria, and provided written informed consent in accordance with applicable regulatory agency and EC requirements.

The data collection at enrolment includes: demographic data, clinical assessment, medical history and co-morbidities, subject information and medical history; subject status and clinical assessment per SOC; and details on previously/currently implanted devices.

Subject information and medical history

- **Demographic data:** age at time of consent; gender.
- **Clinical assessment:** weight, height, BMI, blood pressure, NYHA Class.
- **Medical history / co-morbidities:**
 - **Subject etiology:** ischemic cardiomyopathy; idiopathic cardiomyopathy; valvular cardiomyopathy; hypertrophic cardiomyopathy; congenital heart disease; infiltrative disease; neuromuscular disease (including myotonic dystrophy and Kearns-Sayre syndrome).

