12.1.4.2. Statistical Methods

When the final study subject reaches the final CIP required follow-up visit, the primary analysis will be performed based on the Kaplan-Meier method for the estimation of the 12-month all-cause mortality free-rate (survival rate) including the lower 97.5% confidence bound (computed based on log-log methodology). This Kaplan-Meier analysis will begin at the time of enrolment. Subjects that withdraw consent or are lost-to-follow-up prior to the 12-month endpoint evaluation will be censored at their date of last contact. All subjects actively enrolled will be included in the endpoint analysis.

The null hypothesis will be rejected and the endpoint considered met if the lower 97.5% confidence bound for the all-cause mortality free-rate (survival rate) at 12 months is greater than 80.0%.

Additionally, a Kaplan-Meier survival time-to-event curve along follow-up will be provided.

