12.2. General Statistical Methods

12.2.1. Analysis Sets

All subjects actively enrolled in the study (i.e. who meet all eligibility criteria at the time of enrolment into the study and who have given written informed consent) will be included in the primary endpoints analyses.

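### PM/CRT-P cohort: the survival clock starts at implant but subjects enter only at consent, 0 to 45 days later, so without delayed entry 12-month survival from implant is biased upward

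*Combined protocol and SAP*

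**What the plan says.** The synopsis hypothesis for this cohort is that survival "from implant through 12 months post implant is greater than the pre-specified performance goal of 80.0" percent. Section 12.1.3.1 gives the interval only as 0 to 12 months; the origin comes from the synopsis and from Section 12.1.3.2: "This Kaplan-Meier analysis will begin at the time of implant". Success requires the lower 97.5% log-log bound at 12 months to exceed 80%.

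Entry comes later. Section 11.4: "The enrolment for this registry will occur up to 45 calendar days after the device system implantation". Section 11.1: "The date of signature on the informed consent form is the time point of enrolment". The PM/CRT-P inclusion criteria (Section 9.2.4) allow the same 45-day window, and Section 10.1 has reportable events collected once consent is given.

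The analysis set in Section 12.2.1 is "All subjects actively enrolled in the study", meaning eligible and consented. The only risk-set rule in Section 12.1.3.2 is censoring at last contact for withdrawal or loss to follow-up. Section 12 has no delayed entry, left truncation or landmark.

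For the Non-device cohort, Section 12.1.4.2 puts origin and entry at the same point: "This Kaplan-Meier analysis will begin at the time of enrolment".

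**The concern.** The endpoint is death from any cause. A patient who dies between implant and consent can never be enrolled, so no death can be observed in that interval. The planned estimate nevertheless treats each enrolled subject as at risk from the day of implant. Those days are immortal time: they enlarge the risk set while contributing no possible event.

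The direction follows from the design alone. Unless everyone consents on the day of implant, survival from implant is overstated, and the error favours rejecting the null hypothesis. This affects one of the study's primary tests, against a fixed goal with no concurrent control to share the bias.

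**Working it through.** **1. The plan's own figure.** Inputs (Table 12.1-1): goal 80%, expected 90%, one-sided alpha 0.025, power 90%, attrition 20%. By exact binomial, n = 137 with success at 119 or more survivors gives alpha 0.0245 and power 0.910. Then 137/0.8 = 171.25, rounded up to 172. Both stated numbers reproduce; the sample size arithmetic is not in question.

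**2. What the planned estimate converges to.** A subject who consents at day e has 12-month survival S(365)/S(e), given being alive at e. Under constant hazard with true 12-month survival p, the apparent rate is approximately p^(1 − mean delay/365).

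At p = 0.80:
- day 7: 0.80^(358/365) = 0.803 (+0.3 points)
- mean 9.5 days: 0.80^(355.5/365) = 0.805 (+0.5)
- uniform 0 to 45, mean 22.5 days: 0.80^(342.5/365) = 0.811 (+1.1)
- day 45: 0.80^(320/365) = 0.822 (+2.2)

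At p = 0.90 the same delays of mean 9.5 days, uniform, and day 45 give +0.2, +0.6 and +1.2 points.

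**3. Error of the planned rule.** This was simulated: Kaplan-Meier at day 365, log-log lower 97.5% bound above 80%, deaths possible only after consent, exponential censoring giving 20% attrition per year. The delay distributions are assumptions. The 9.5-day case is an exponential with scale 10 days truncated at 45, which puts 51% of consents within 7 days. N = 172, true survival 80%, constant hazard, 60,000 trials per cell:

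| Implant-to-consent delay | Mean estimate | One-sided error |
|---|---|---|
| None | 80.0% | 1.8% |
| All at day 7 | 80.3% | 2.4% |
| Mean 9.5 days | 80.5% | 2.7% |
| Uniform 0 to 45 days | 81.1% | 4.0% |
| All at day 45 | 82.2% | 7.9% |

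Smaller repeat runs agree to within simulation error. At N = 200 the last three rows are about 3%, 4 to 5% and 9 to 10%.

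**4. If deaths cluster early.** Constant hazard puts 45/365 = 12% of the 12-month hazard in days 0 to 45. If that share is 20%, the error at N = 172 is about 3.1% (mean 9.5 days) or 6.4% (uniform). With a Weibull shape of 0.7 and uniform delay, the bias is +2.5 points and the error about 9.4%. The documents do not give the early hazard, and the cohort mixes first implants with replacements.

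**5. With delayed entry, N = 172.**

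| Delay and hazard | Estimate at true 80% | Error | Power at true 90% |
|---|---|---|---|
| Mean 9.5 days, constant | 80.0% | 2.0% | about 90% |
| Uniform, constant | 80.0% | 2.4% | about 86-87% |
| Uniform, 20% in days 0 to 45 | about 80% | 2.8% | about 84% |

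With no delay, power under the planned rule is about 92%.

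**The case against.** **The estimand may be survival among enrolled subjects.** The synopsis analysis method describes "the proportion of actively enrolled subjects who are alive 12 months after implant". For that conditional population the planned estimate is consistent, so part of the problem is labelling. But the synopsis hypothesis is about treated subjects from implant, and the goal is fixed at 80%, described under Table 12.1-1 as a "clinically accepted delta of 10%, subtracted from expected performance". Nothing says that the expected performance is conditional on surviving to a later consent. The wording therefore does not remove the mismatch. The time origin of the cited benchmark study is not in the documents, so its match to either origin cannot be settled here.

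**The effect is small in likely use.** This largely stands. The log-log rule starts below nominal, so short delays keep the error near 2.5%, and at a true 90% the bias is minor. The figure near 8% needs every subject to consent on day 45, and delayed entry could not repair that case.

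**A reader might infer that the ICD and CRT-D analyses carry the same bias**, since Sections 12.1.1.2 and 12.1.2.2 also start at implant. The documents do not support that. Their endpoint is a first treated arrhythmia or life-threatening arrhythmic symptoms. A subject with a treated arrhythmia before consent can still enrol unless it caused hemodynamic instability (Section 9.3.2), and device data are collected at enrolment. Whether such events count is a separate question, on which Sections 10.1, 20.1 and the event committee's own procedures (Section 22.2) bear.

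**Conclusion.** The mismatch between time origin and entry in Section 12.1.3.2 is real, is confined to the PM/CRT-P cohort, and pushes toward meeting the goal. The direction is certain; the size is not, because it rests on assumed delays and an assumed hazard shape. Under constant hazard the error ranges from about 2% to about 8%, with about 4% when delays fill the permitted window evenly; it is higher if deaths cluster early. It matters mainly if true survival lies near 80%. A reader might go further and infer that the primary result would be unreliable at the planned 90%. The figures do not support that: a bias of 0.2 to 1.2 points under constant hazard is small beside a 10-point margin. It should be fixed, because it affects a primary test and the dates needed are already collected.

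**What to change.** In Section 12.1.3.2, keep the implant origin and the synopsis hypothesis. Specify a delayed-entry (left-truncated) Kaplan-Meier estimate with the log-log bound, each subject joining the risk set on the consent date. Report the distribution of implant-to-consent delay and the numbers at risk over days 0 to 45. Label the result as conditional on survival to the first day with subjects at risk, because delayed entry cannot recover days when nobody is under observation: if all consent on day 45 it still returns 82.2% for a true 80%.

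The alternative is to start the clock at enrolment, as Section 12.1.4.2 does, and to restate the hypothesis and goal for that origin. Without the restatement a mismatch remains: with uniform delay and 20% of the hazard in days 0 to 45, the error against the implant hypothesis is still about 3.4%.

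Implant date (Section 11.4) and consent date (Section 11.1) are already collected, so the change to text and code is small. The cost is power, because early risk sets are thin. The stated 90% power for the 172 minimum should be restated: about 90% with a mean delay of 9.5 days, 86-87% with uniform delay and constant hazard, 84% if risk is front-loaded. At 200, the cohort's upper limit, it is about 90% and 88% in the two uniform cases. Raising the 172 minimum would also raise the 556 total (117 + 95 + 172 + 172). Delayed entry does not guarantee the nominal error: it is about 2.8% with front-loaded risk and uniform delay, and 3.5% with a Weibull shape of 0.7.
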